This is a non-randomized, open-label, non-blinded, 10-week pilot study of a novel intervention, namely, non-contact karate, for early to middle stage PD. The intervention—namely, karate classes—are developed for and will include only patients with Parkinson's disease. Eligible subjects will engage in twice-weekly karate classes for 10 weeks, specifically designed for individuals with early to middle stage PD, focused on incorporating upper and lower limb movements in multiple directions, increasing awareness throughout the body, shifting body weight and rotation, relaxation of the muscles, improving reaction time, using complex repetitive actions to improve coordination, footwork training and centered weight shifts to help with fall prevention, and striking shields for self-defense and stress relief.

Each subject will attend a pre-intervention focus group, at which time the study logistics will be reviewed, informed consent process will occur, the subject will complete a brief, individual pre-intervention assessment focused on overall mobility, gait, balance, attention, mood, and quality of life, and the subjects will be prompted to share aloud their thoughts on exercise, balance, and mindfulness practices in general and in PD specifically, and any expectations or preconceptions that they have regarding karate classes for PD. The focus group sessions will be audiotaped. After the sessions the information recorded will be transcribed into electronic documentation for later review and analysis. At the end of the study, the audiotapes will be destroyed.

Following 10 weeks of twice weekly classes, the subjects will have a post-intervention assessment and focus group, in which the pre-intervention assessments (TUG, FRT, TMT, PDQ-8, HADS, SDMT, DST) will be re-administered, along with the PGIC for the subject's global impression of change. Subjects will be prompted to share their thoughts on how the intervention impacted their overall wellbeing, balance, and mindfulness; whether the intervention achieved their expectations; and they will be asked to provide feedback for improvements. Finally, the study team will contact subjects 6 months post-intervention to assess continued engagement in karate or related activities and again, the subject's quality of life and global impression of change.

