The PI and research team will collaborate with a professor of Cinema and Television Arts from Columbia College Chicago, IL to develop a documentary to educate others about karate as an interactive form of exercise and its potential benefits on the symptoms and quality of life of people with PD. To capture the groups' journey over 10-weeks, portions of the pre-intervention focus group, the karate classes, and the post-intervention focus group will be videotaped. For a more in-depth look, two to three subjects will be followed during the entire study and interviewed to provide a personal narrative of their experiences with the karate classes and living with PD. The interviews will be videotaped.

We will recruit 30 individuals with PD diagnosed by a neurologist, ages 30-90, living in Chicago, and with Hoehn & Yahr (HY) stage 1 (unilateral symptoms, no balance issues), stage 2 (bilateral symptoms, no balance issues), or stage 3 (bilateral symptoms, some postural or balance involvement). Subjects will be assigned to one of two cohorts of 15 subjects each, based on dojo location and class schedule. For example, one cohort may take classes Tuesday and Thursday nights at the Wilmette dojo, and the second cohort may take classes Wednesday and Saturday mornings at the Glenview dojo, however class times and locations are to be determined.

II. Characteristics of the Research Population

II.a. Number of Subjects

Total Number of Subjects: 30

This is a pilot study; our power analysis (see table below) is based on the TUG, with the following assumptions: mean TUG score for individuals with PD is 14.8 seconds with standard deviation of 5.8 seconds, alpha of 0.05, and correlation between baseline and follow-up assessments of 0.5. We calculated sample sizes necessary with various minimum clinically important difference values for the TUG, which ranges from 2 seconds to 5 seconds in various studies^{1,18}, and varying for power between 80-90%. With a sample size of 30, we will have 80% power to detect a change of 3 seconds in the TUG, and will be more than 90% powered to detect a change of 4 seconds or greater.

| Baseline mean TUG | Baseline SD TUG | Min. clin. Important difference | Correlation b/w baseline, follow-up | Power | Sample size |
|-------------------|-----------------|---------------------------------|-------------------------------------|-----------|-------------|
| 14.8s | 5.8 | 2s | 0.5 | .9 | 89 |
| | | | 0.5 | .8 | 67 |

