| 14.8 | 5.8 | 3s | 0.5 | .9 | 40 |
| | | | 0.5 | .8 | 30 |

| | | | | | |
|------|-----|----|-----|----|----|
| 14.8 | 5.8 | 4s | 0.5 | .9 | 23 |
| | | | 0.5 | .8 | 17 |
| 14.8 | 5.8 | 5s | 0.5 | .9 | 15 |
| | | | 0.5 | .8 | 11 |

II.b. Gender of Subjects

There will be no exclusion of subjects based on gender.

II.c. Age of Subjects

Subjects will be 30-90 years of age.

II.d. Racial and Ethnic Origin

There will be no exclusion of subjects based on racial or ethnic characteristics. However, subjects must be fluent in English to participate in the karate classes, as that is the language of instruction, and due to the general lack of appropriately translated neurological and neuropsychological assessments and appropriate normative comparison samples. These factors are critical for accurate administration, scoring, and interpretation of neurological and neuropsychological test data.

II.e. Inclusion Criteria for All Subjects:

1. Each subject must be between 30-90 years of age. A subject may be of either gender, any race/ethnicity.
2. Subjects will be those diagnosed with Parkinson's Disease by a treating neurologist; if the subject is seen at Rush University Medical Center, this will be verified via chart review. If the subject is seen elsewhere, he or she will be asked to have their neurologist sign a form confirming the diagnosis of Parkinson's Disease and indicating the subject's HY stage (with definitions of each stage provided on the form for providers who may not be familiar with HY staging) at the most recent visit, to be sent back to the study coordinator for eligibility verification.
3. English speaking.
4. Living within the Chicago area.
5. Subjects may be untreated for Parkinson's Disease, or may be taking any individual PD medication or combination thereof. Subjects may or may not have had Deep Brain Stimulation. Subjects may or may not be receiving physical or occupational therapy. Subjects will be encouraged to maintain their same medication regimen throughout the duration of the 10-week study, however if emergent issues arise requiring medication changes, the subject will not be disqualified.

II.f. Exclusion Criteria for All Subjects

1. Subjects requiring an assistive device (cane, walker, wheelchair) or the assistance of another person in order to ambulate.
2. Subjects with active psychosis or exhibiting symptoms of a severe psychiatric disorder.

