Subjects will then complete a brief demographic questionnaire, including duration of PD diagnosis in years, baseline activity level, prior involvement with karate or other martial arts, number of falls in the past 12 months, and subjects will complete the Parkinson's Disease Questionnaire-8 (PDQ-8)¹⁹, a brief, validated, PD-specific 8-item measure of quality of life. Subjects will complete the Hospital Anxiety and Depression Scale (HADS). Subjects will also write their response to the open-ended prompt, "What do you hope to achieve in this class?"

Subjects will then meet with a study team member to complete the TUG (see description below), FRT, and TMT. Next, the subject will meet with the PI or another study team member in a private room for a brief assessment of bradykinesia, tremor, rigidity, and postural stability in order to determine baseline HY stage. Lastly, subjects will meet with a study team member to complete short attention assessments with a SDMT and DST. Once all subjects have completed the pre-intervention written and physical assessments, the focus group will commence.

Subjects will be prompted to share aloud their thoughts on exercise, balance, and mindfulness practices in general and in PD specifically, and any expectations or preconceptions that they have regarding karate classes for PD.

Intervention

Each karate class will follow a structured curriculum, as shown in Appendix 1, with complexity of movements and movement patterns increasing over the 10-week study period. Classes will take place twice weekly, and subjects will be required to attend their assigned class time/location. Each class will last approximately 45-60 minutes. Attendance will be recorded in hard copy by the instructors at each class, with recordings only of the subject's name, not linked to their unique study ID; the attendance log will be shared with the study coordinator following the final class. A member of the study staff will be present at each class in order to answer questions and to support participants and instructors should any questions about protocol or PD safety arise.

Post-intervention focus group

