In the week prior to the 10th class, the study team will contact subjects to remind them of the date and time of the final class and the post-intervention focus group. The post-intervention assessment will consist of a repeated TUG, FRT, TMT, HADS, PDQ-8, SDMT, DST, brief question about falls in the past 10 weeks, and PGIC. Each subject will receive their initial response to the "What do you hope to achieve in this class?" prompt, and will be asked to reflect in a written, open-ended manner on whether they feel that they achieved their goal. In addition, subjects will indicate their response to the following questions regarding feasibility: "Would you recommend this program to someone else with PD?" and "If available, would you continue to participate in this or a similar karate class?"

Subjects will then participate in a focus group, similar to the pre-intervention focus group, in which they be asked to share and reflect on how the intervention affected their overall attitude towards exercise; how it affected their balance and falls; how it affected their mindfulness; any other positive or negative benefits; any impact on their care partner(s) (if applicable); and suggestions for changes to the intervention for the future. Depending on availability of space, the post-intervention focus group may take place at Rush University, or may take place immediately following the last class at the respective dojo.

Documentary

Portions of the focus groups and karate classes, and the entire in-depth interview will be videotaped by the Columbia filmmakers using personal equipment. Subjects may choose to not participate in the documentary project which means subjects will not participate in the in-depth video interviews, and they will not be included in individual or group video shots during the focus groups and karate classes. To ensure confidentiality, subjects will be placed in one of two groups, Group A or Group B, depending on whether they decide to participate in the documentary or not. Subjects who agree to be videotaped and possibly interviewed will be part of Group A while subjects who choose not to be videotaped or interviewed will be in Group B. Subjects may not switch groups after the study begins with the pre-intervention focus group. Participation in the karate classes and focus groups will not be affected if a subject does not wish to be videotaped or interviewed. Subjects will not be penalized if they decide to not take part in the documentary

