Six month follow-up phone call

The study team will contact the subjects by phone six months after the final class to ask whether the subject has continued to participate in any structured karate or martial arts classes; if yes, frequency and location will be asked. If no, reasons for lack of participation will be asked. Finally, PGIC will be administered a final time.

Assessments: Subjects who agree to be part of the study and sign the Informed Consent Form will be asked to complete a series of assessments to assess their current neurological status and overall wellbeing. There is no known risk associated with participation in these assessments, and they are a part of routine clinical care for these conditions. These tests are typically experienced as interesting to subjects. Administration of these assessments should take 15 minutes per subject immediately prior to the first class, and 15 minutes per subject immediately after the final class. All or some of the following assessments and self-report measures may be administered but are not limited to:

- *Demographic/disease questionnaire:* This brief, one-page questionnaire will ask for the subject's name, phone number (for 6-month follow-up call), age, gender, race, ethnicity, PD duration in years, prior exposure to karate or martial arts classes, baseline activity level, and number of falls in the past 12 months. There will be one open-ended question asking, "What do you hope to achieve in this class?"
- *Hoehn and Yahr Scale (HY):* A system used for describing how Parkinson's symptoms progress and the relative level of disability. There are five stages: Stage 0 – No signs of disease; Stage 1 – Unilateral disease; Stage 1.5 – Unilateral plus axial involvement; Stage 2 – Bilateral disease, without impairment of balance; Stage 2.5 – Mild bilateral disease with recovery on pull test; Stage 3 – Mild to moderate bilateral disease; some postural instability; physically independent; Stage 4 – Severe disability; still able to walk or stand unassisted; Stage 5 – Wheelchair bound or bedridden unless aided.²⁰

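### Medication timing is neither matched nor recorded at the two mobility test sessions, so a systematic shift in medication state would be read as a karate effect or would hide one

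*Combined protocol and SAP*

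**What the plan says.** All references are to the combined protocol and SAP.

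- **Who is tested.** Section II.e, criterion 5, admits untreated subjects and subjects who "may be taking any individual PD medication or combination thereof". DBS and ongoing physical or occupational therapy are also allowed. Subjects are encouraged to keep the same regimen for the 10 weeks, and changes for emergent problems are permitted.
- **Baseline session.** Section III, Pre-Intervention Focus Group: "Subjects will then meet with a study team member to complete the TUG (see description below), FRT, and TMT". The listed questionnaire items cover disease duration, activity, martial-arts exposure and falls. They contain no medication item.
- **Repeat session.** Section III, Post-intervention focus group, repeats the same tests. On location it says: "Depending on availability of space, the post-intervention focus group may take place at Rush University, or may take place immediately following the last class".
- **Timing.** The Assessments text in section III allots "15 minutes per subject immediately prior to the first class, and 15 minutes per subject immediately after the final class". A class lasts roughly 45 to 60 minutes (section III, Intervention).
- **How TUG is standardised.** The TUG description fixes the chair, the distance, the pace and the stopwatch. It is silent on the subject's medication state.
- **Design and analysis.** Section I.c: "This is a non-randomized, open-label, non-blinded, 10-week pilot study of a novel intervention". Section III.b analyses change with a paired t-test or Wilcoxon test, stratified by Hoehn and Yahr stage. No medication or timing variable enters.

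**The concern.** TUG, the functional reach test and the Tinetti test measure motor performance in people whose performance may vary over the medication day. The plan controls, loosely, which drugs a subject takes over 10 weeks. It does not control where in the dosing day the subject stands when tested. A subject with a perfectly stable regimen can therefore be tested soon after a dose at one session and late in the interval at the other. The problem remains if the repeat is held on a non-class day, so it is separate from acute exercise or fatigue.

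The before-class and after-class anchors do not bring the sessions together. If both use the same class slot, the repeat falls later in the day by at least the length of the class, for the whole cohort. That is a common offset in clock time, not scatter.

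Hypothesis 1 and the sample size both rest on the within-subject change in TUG. With one arm, that change contains whatever the medication state contributed. Without dose and test times on file, nobody can later check or adjust for it.

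**Working it through.** **1. The plan's own figure.** Section II.a assumes "mean TUG score for individuals with PD is 14.8 seconds with standard deviation of 5.8 seconds", with "alpha of 0.05, and correlation between baseline and follow-up assessments of 0.5".

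- SD of change = 5.8 × √(2 × (1 − 0.5)) = 5.8 s.
- Normal approximation, two-sided 5%, 80% power, 3 s: n = (5.8 × (1.960 + 0.842) / 3)² = 29.3, rounded up to 30.

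This agrees with the stated 30: "With a sample size of 30, we will have 80% power to detect a change of 3 seconds in the TUG". All eight rows of the table reproduce in the same way (89, 67, 40, 30, 23, 17, 15, 11). A noncentral-t calculation gives 78.2% power at N = 30, and that is the reference below. The smallest significant mean change is 2.045 × 5.8 / √30 = 2.2 s.

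**2. Offset built into the schedule.** If both sessions use the same slot, baseline ends before the class starts and the repeat begins after it ends. The gap in clock time is at least 45 to 60 minutes. It is larger if the baseline focus group falls between testing and the class. It is unknown if the repeat is done at Rush.

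**3. Assumptions.** The documents give no size for a medication-state effect on TUG. For illustration, assume:

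- TUG differs by d = 2 to 3 s between a good and a poor state.
- A share p = 20-40% of subjects are in different states at the two sessions.
- The net excess in one direction is 10-20% of subjects.

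**4. Systematic shift.** Net shift in mean change = net excess × d, which runs from 0.10 × 2 = 0.2 s to 0.20 × 3 = 0.6 s. This is 7-20% of the 3 s target. Power is from the noncentral t with 29 degrees of freedom and noncentrality (mean change / 5.8) × √30.

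| Net shift (s) | False significant improvement, karate null | Power for a true 3 s gain if the shift is adverse |
|---|---|---|
| 0 | 2.5% | 78% |
| 0.2 | 3.8% | 72% |
| 0.6 | 7.9% | 59% |

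**5. Shifts that average zero.** Added variance = p × d².

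- 0.2 × 2² = 0.8, so SD of change = √(33.64 + 0.8) = 5.87 s and power for 3 s is 77%.
- 0.4 × 3² = 3.6, so SD of change = √(33.64 + 3.6) = 6.10 s and power is 74%.

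There is no bias in this case.

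**The case against.** The strongest reply is that the documents show an omission, not an effect. A reader might infer that a medication shift is in fact being counted as benefit. The documents do not support that. Only a shift with a non-zero mean biases a paired mean, and nothing shows that one occurs or in which direction. This objection stands, and the point has to be conditional.

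A reader might also multiply 15 subjects by 15 minutes and infer a queue of 225 minutes that alone scrambles dose-to-test intervals. That is total subject-time. Section III names a principal investigator, a coordinator and research assistants, and describes successive stations, so the actual wait is unknown and could be much shorter. The queue is no evidence for the point.

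The schedule may also match better than it first appears. Each cohort has an assigned class time, and a same-slot offset may be only about an hour. The Rush-or-dojo sentence is about where the focus group is held. Even so, no section requires the same slot, and an hour can matter or not depending on the dose time, which is not recorded.

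The sizes are assumed and modest, and a 0.6 s shift is well short of the 2.2 s needed for significance. Mean shifts of 1 to 2 s would put the false-improvement rate at 15-45%, but nothing in the documents supports shifts that large. The planning correlation of 0.5 may already include some mismatch noise, so adding variance may double-count. Untreated subjects have no dose-related shift and dilute any mean effect. All of this stands and limits the size. None of it closes the gap.

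**Conclusion.** The gap is real and worth correcting. Following the schedule exactly gives pairs of motor tests that are not matched on medication state and cannot be checked afterwards, in a design with no control arm. If a shift is systematic, it would be counted as a karate effect or would hide one. If it averages zero, it costs precision only.

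Under the assumed ranges the size is moderate: a false-improvement rate of about 4-8% instead of 2.5%, power of 72-59% instead of 78% under the opposite shift, or 77-74% under random mismatch. These figures rest on assumed state differences and mismatch rates, not on the documents, and the random-mismatch loss may be partly in the planning correlation already.

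A reader might take this as an error in the sample size. It is not: the power table reproduces in full. The point concerns how the test sessions are standardised.

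**What to change.** In section III (Pre-Intervention Focus Group, Post-intervention focus group and Assessments):

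1. At both sessions, record the time of the last Parkinson's medication dose, the time of the test, self-rated on/off state, and DBS on/off. Mark untreated subjects as not applicable for dose time.
2. Where feasible, schedule each subject's post-intervention tests at a similar interval since the last usual dose as at baseline, with a similar clock time as the practical means. Exact matching on both, or a fixed testing order, would be too rigid for a group session.
3. In section III.b, pre-specify a supportive, descriptive display of TUG change by whether the two sessions were matched, and define matched before the data are seen. State that the matched subset has less power. If 60-80% of 30 subjects are matched (18 to 24), power for 3 s is about 54-68% by the same noncentral-t calculation.

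The medication regimen is not altered. The cost is a few extra case report form fields and less flexibility in scheduling the final session. If scheduling proves impractical, item 1 alone is still worth doing, because dose and test times cannot be reliably recovered later.

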The qualitative data from the focus groups will be audio-recorded and transcribed, with all identifying information stripped from the transcripts. Once transcribed, the audio recordings will be destroyed. The qualitative data will be analyzed using a grounded theory approach to identify pertinent themes, with data stored as password-protected files behind the Rush firewall, accessible only to study staff.

All video footage will be the sole property of the PI. Videos will have identifying information (i.e. image of patient's face, first name). Video files will be stored and password-protected behind the Rush and the Columbia firewall. The video along with the data collected from the focus groups and karate classes may be used as part of the dissemination of the study results and for educational purposes.

The PI, co-investigators, and/or study staff will review all data collection forms on an ongoing basis for data completeness and accuracy as well as protocol compliance. The data will be reviewed on a quarterly basis:

- Subject accrual (including compliance with enrollment criteria)
- Status of all enrolled subjects
- Adherence data regarding study visits and procedures

Safety data (AEs and SAEs) will be reported to the Principal Investigator and reviewed per occurrence and in accordance with the IRB's regulations. Any significant findings (i.e. protocol deviations) will be reported to the IRB in accordance with requirements and will be documented accordingly.

III.c. Data Storage and Confidentiality

All subjects will be assigned unique ID numbers. All research data files will be stored at the Rush University Parkinson's Disease and Movement Disorders Program in secured file cabinets, including hard copies of case report forms, informed consent forms and informed consent documentation checklists. Data will be entered into a secured database (REDCap). The database will be stored on a secure password-protected server and not on individual desktop computers. The code sheet will be password protected and the password will be updated annually. Hard copies of case report forms and informed consent documentation checklists will be labeled with the study ID only and maintained in individual files by study ID number. Signed informed consent forms, containing subject names, will be stored separately in the regulatory binder, which will be stored in a locked file cabinet in the PI's office. Class

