attendance records will be maintained using name only, not subject ID, by the class instructors. These records will then be given to the study coordinator following the final class, who will then link the attendance information with the subjects' data using the code sheet. Attendance information will be entered into REDCap, after which time, the hard copies of the attendance information will be destroyed.

Before videotaping begins, subjects who agree to participate in the documentary must sign their name on the informed consent form. Participating in the documentary is voluntary. Informed consent forms will be stored in the regulatory binder, which will be stored in a locked file cabinet in the PI's office. The PI and the Columbia Cinema and Television Arts filmmakers will have access to the video files to perform activities only related to the study.

Only the PI and research staff will have access to the database and hard copies of study documents. Data will be stored in a format suitable for research inquiries by the PI who might make use of the data in a retrospective manner for other Rush-based research studies. If a particular researcher/collaborator has an interest in a study population, then the PI will review the database to identify eligible subjects that meet the study inclusion criterion and the potential participant(s) will then be contacted by a member of this study team whom the subject has already met to see if they are interested in participating in the particular study. If a participant is interested, he or she will be referred to that Rush study team and will be scheduled for a separate consent procedure with the individual Rush researcher for that particular study and at that point the participant can choose whether to participate or not in that particular study. The results of the Karate for PD study may be published in a book, journal, and other media or used for teaching purposes. However, all published data will be made anonymous.

IV. Risk/Benefit Assessment

IV.a. Risk

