There are no known risks from participating in neurological or neuropsychological tests. Subjects may experience mild boredom or cognitive fatigue; however, most individuals with like symptoms find the tests interesting and are able to tolerate up to two-hour duration of testing well. There is, however, a risk of falls or injury associated with participation in any exercise, including karate, for which subjects will sign a liability waiver used for all karate class participants at the Fonseca Martial Arts dojos. The risks will be minimized to the extent possible by 1) having all instructors undergo basic instruction in principles of PD by the PI prior to the first class; 2) having all classes held at quieter times in the dojo, so as to avoid overcrowding and risks of falls or freezing of gait in crowded, busy situations; 3) having small instructor to subject ratios (2 instructors per 15 subjects) to allow for maximal supervision and guidance; 4) having study staff present to assist with mobility issues at as many classes as possible.

Another possible risk is the loss of confidentiality by participating in the video because the subject's image may be captured. However full names will not be used during interviews with the two or three subjects who agree to answer questions about their experiences with the karate classes.

IV.b. Potential Benefit to Subjects

Potential benefits to subjects include the following: 1) cognitive and physical improvements in PD symptoms related to both vigorous physical activity and mindful exercise; 2) benefits of mindful exercise on quality of life; 3) the enjoyment of participating in a new activity in a social environment with other individuals with PD; 3) the satisfaction of learning a new skill; 4) the knowledge that by participating,

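### Falls and injury are the named risk of the classes, yet falls are asked about only at the final session, subjects who stop early are not asked, and no falls or adverse-event summary is planned

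*Combined protocol and SAP*

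**What the plan says.** Section IV.a identifies "a risk of falls or injury associated with participation in any exercise, including karate". The opening statement of aims includes falls among the outcomes assessed before and after the classes, and section I.c admits Hoehn & Yahr stage 3 subjects, who have some postural or balance involvement.

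Four places bear on how a fall or injury would be captured once classes begin:

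- **At class** (section III, Intervention): "Attendance will be recorded in hard copy by the instructors at each class", and "the attendance log will be shared with the study coordinator following the final class". Section III.c adds that, once attendance is entered in REDCap, "the hard copies of the attendance information will be destroyed". A study staff member is to be present to answer questions and give support.
- **At the end** (section III, Post-intervention focus group): the assessment includes a "brief question about falls in the past 10 weeks", and the group discussion that follows touches on balance and falls.
- **At six months** (section III, Six month follow-up phone call): continued participation in karate or martial arts, reasons if there is none, and the PGIC.
- **Throughout** (section III.b): "Safety data (AEs and SAEs) will be reported to the Principal Investigator and reviewed per occurrence".

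The analysis text in section III.b covers seven scales, attendance, PGIC, goal attainment, willingness to continue or recommend, and later participation. It mentions neither falls nor adverse events.

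**The concern.** The harm that the protocol itself expects is solicited once, at the end, from those who come to the final session. Someone hurt in week 3 who stops attending is not there to answer. If being hurt makes stopping more likely, the people left out are those with the most to report.

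The final question also omits injury and does not separate falls in class from falls elsewhere, so even a complete set of answers could not say what happened during the classes.

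What is at stake is the feasibility conclusion. The third hypothesis defines feasibility by attendance and willingness to continue or recommend. Without systematic capture of harm, the pilot may be unable to say whether people who stopped did so because they were hurt, and an event not recorded at the time is hard to recover later.

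**Working it through.** The plan gives no fall, injury or dropout figure, so there is none to reproduce. Its one design calculation concerns the TUG and does not enter here. The check is a reading of the procedures, followed by an illustration.

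**1. Follow one subject.** Suppose a subject is hurt in week 3 and does not return.

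| Contact | What it would yield |
|---|---|
| Class log | Absence from later classes; no event field is described |
| Study staff at class | May see the event; no recording duty is stated |
| Reminder before the final session | Date and time only |
| Post-intervention falls question and focus group | Nothing, because the subject is absent |
| Quarterly review (III.b) | Status and adherence; a quarter is about 13 weeks, longer than the 10 weeks of classes |
| Six-month call | Reasons for not participating; no falls or injury item |
| AE/SAE route (III.b) | The event, if someone reports it |

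No described contact asks this subject about a fall or an injury. Only the last row is meant to carry one. The text gives that route no definition of an event, form, responsible recorder, schedule for asking, or follow-up of subjects who stop.

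**2. Compare the two statements on staff.** The Intervention section has a study staff member at each class. Section IV.a says staff will be present at as many classes as possible. These differ and must be reconciled.

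**3. Compare aims and analysis.** Falls are a listed assessment in the aims. Section III.b plans no summary of them.

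**4. Illustrate the size.** The 30 subjects come from section II.a; every rate below is an assumption. Suppose 3 of 30 are injured in a fall (10%). Each injured subject stops before the final session with probability q, and 10% of the 27 uninjured also stop. The final question is the only capture, and completers answer it accurately.

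- Expected injured completers: 3(1 − q)
- Expected uninjured completers: 27 × 0.9 = 24.3
- Proportion among completers: 3(1 − q) / [3(1 − q) + 24.3]
- Chance of missing at least one injured subject: 1 − (1 − q)³

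| q | Injured completers | All completers | Proportion seen | Chance of missing at least one |
|---|---|---|---|---|
| 0.25 | 2.25 | 26.55 | 8.5% | 58% |
| 0.50 | 1.50 | 25.80 | 5.8% | 88% |
| 0.75 | 0.75 | 25.05 | 3.0% | 98% |

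If q is 0.10, the same as for uninjured subjects, the result is 2.7/27 = 10%, which is no understatement of the proportion. The bias therefore comes from harmed subjects stopping more often, not from dropout as such. Any event recovered through the AE/SAE route would shrink the gap, by an amount that the documents do not allow one to estimate.

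**The case against.** The strongest reply is that section III.b already provides a route that does not depend on reaching the last session. A fall in class would usually be seen by study staff or an instructor, and adverse events then go to the principal investigator as they occur. The six-month call is to the subjects, not only to completers, and its question on reasons for not participating could bring an injury to light. The focus group gives those present an open prompt. This is also a 30-subject, single-arm pilot classed as minimal risk, and its case report forms are not shown.

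Much of this stands, and it rules out several stronger readings that a reader might infer:

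- **That the class sheet bars recording of events.** The phrase "with recordings only of the subject's name, not linked to their unique study ID" is a rule about the identifier. Section III.c confirms this by contrasting name with subject ID. The log is for attendance and no event field is described, but nothing forbids one.
- **That the safety review has no input at all.** Staff at class and the AE/SAE sentence give it some. What is missing is a stated recording duty and any procedure for asking subjects who stop.
- **That falls are asked about only once.** Baseline also asks for falls in the past 12 months. The end question is the only one covering the study period.
- **That nothing else is recorded at class.** Portions are filmed for the documentary, but subjects who decline are not filmed, and the footage is not a safety record.
- **That the trial's harm rate is biased.** The plan states no harm rate. The tendency applies to any solicited falls count that is later reported.

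The reply does not show that anyone asks a non-completer about falls or injury, or that the results will be summarised.

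**Conclusion.** The point holds as a gap in procedure and reporting. Followed as written, the plan solicits falls from completers only, does not solicit injuries by any specific question, describes no recording of either at class beyond the general AE/SAE sentence, and plans no summary.

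A solicited falls count would tend to understate harm if harmed subjects are more likely to stop, less whatever the AE/SAE reports recover. The real size is unknown. The range of 3.0% to 8.5% against a true 10% rests wholly on the assumed rates and on the final question being the only capture, so it shows direction and plausible scale and is not an estimate for this trial.

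This is a cheap improvement, not a flaw that undermines the TUG, PGIC or attendance results. Confidence is medium, because the case report forms and the removed pages may hold more than the text describes.

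**What to change.** 1. **Record events at class.** Have the study staff member present, or the instructor if none is, complete a short dated fall and injury entry by study ID on a form that is retained. Pass any event to the principal investigator under section III.b. Keep this form apart from the attendance sheet, which carries names and is destroyed after entry. Instructors work by name, so the coordinator would need to supply IDs for any entry an instructor makes.
2. **Ask everyone at the end.** Split the post-intervention item into falls in class, falls outside class, and injuries. Ask it by phone, with the reason for stopping, of every enrolled subject who stopped or missed that session.
3. **Plan the summary.** Add to section III.b a descriptive summary of falls and injuries for all subjects who attended at least one class, with class events per session attended. At full attendance there would be 30 × 20 = 600 subject-sessions, and at 75% attendance 450. These are clustered within 30 people and two cohorts, so give no per-session confidence bound that treats them as independent.
4. **Reconcile** the Intervention section and section IV.a on staff presence at classes.

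The cost is a short form, a few phone calls, a little more paperwork, and a harm rate that may look less favourable. No extra staff are needed.
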